6.4.4 Response Criteria

6.4.4.1 Evaluation of target lesions*

Complete Response (CR): Disappearance of all target lesions. Any pathological lymph nodes (whether target or non-target) must have reduction in short axis to <10 mm.

Partial Response (PR): At least a 30% decrease in the sum of diameters of target lesions taking as reference the baseline sum diameters.

Progression (PD): At least a 20% increase in the sum of diameters of target lesions taking as reference the smallest sum on study (this includes the baseline sum if that is the smallest on study) or the appearance of one or more new lesions.

Stable Disease (SD): Neither sufficient shrinkage to qualify for PR nor sufficient increase to qualify for PD taking as references the smallest sum diameters while on study.

*All measurable lesions up to a maximum of 5 lesions (and a maximum of 2 lesions per organ) representative of all involved organs should be identified as **target lesions** and recorded and measured at baseline. Target lesions should be selected on the basis of their size (lesions with the longest diameter), be representative of all organs involved, and be suitable for accurate repetitive measurements (either by imaging techniques or clinically). A sum of the diameters (longest for non-nodal lesions, short axis for nodal lesions) for all target lesions will be calculated and reported as the baseline sum diameters. The baseline sum diameters will be used as reference to further characterize the objective tumor response of the measurable dimension of the disease.

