3.9.1 Off Treatment Criteria

- Progressive Disease
- Excessive toxicity as defined in section **3.3**
- Allergic reaction to investigational agent
- The subject becomes pregnant
- PI discretion
- Patient request to be withdrawn from study

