6.4.2 Disease Parameters

Measurable disease: Measurable lesions are defined as those that can be accurately measured in at least one dimension (longest diameter to be recorded) as ≥ 20 mm by chest x-ray, as ≥ 10 mm with CT scan, or ≥ 10 mm with calipers by clinical exam. All tumor measurements must be recorded in millimeters (or decimal fractions of centimeters).

Malignant lymph nodes. To be considered pathologically enlarged and measurable, a lymph node must be ≥ 15 mm in short axis when assessed by CT scan (CT scan slice thickness recommended to be no greater than 5 mm). At baseline and in follow-up, only the short axis will be measured and followed.

Non-measurable disease. All other lesions (or sites of disease), including small lesions (longest diameter < 10 mm or pathological lymph nodes with ≥ 10 to < 15 mm short axis), are considered non-measurable disease. Bone lesions, leptomeningeal disease, ascites, pleural/pericardial effusions, lymphangitis cutis/pulmonitis, inflammatory breast disease, and abdominal masses (not followed by CT or MRI), are considered as non-measurable.

Note: Cystic lesions that meet the criteria for radiographically defined simple cysts should not be considered as malignant lesions (neither measurable nor non-measurable) since they are, by definition, simple cysts.

‘Cystic lesions’ thought to represent cystic metastases can be considered as measurable lesions, if they meet the definition of measurability described above. However, if non-cystic lesions are present in the same patient, these are preferred for selection as target lesions.

Target lesions. All measurable lesions up to a maximum of 2 lesions per organ and 5 lesions in total, representative of all involved organs, should be identified as **target lesions** and recorded

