6.4.3 Methods for Evaluation of Measurable Disease

All measurements should be taken and recorded in metric notation using a ruler or calipers. All baseline evaluations should be performed as closely as possible to the beginning of treatment and never more than 4 weeks before the beginning of the treatment.

The same method of assessment and the same technique should be used to characterize each identified and reported lesion at baseline and during follow-up. Imaging-based evaluation is preferred to evaluation by clinical examination unless the lesion(s) being followed cannot be imaged but are assessable by clinical exam.

Clinical lesions: Clinical lesions will only be considered measurable when they are superficial (e.g., skin nodules and palpable lymph nodes) and ≥ 10 mm diameter as assessed using calipers (e.g., skin nodules). In the case of skin lesions, documentation by color photography, including a ruler to estimate the size of the lesion, is recommended.

Chest x-ray: Lesions on chest x-ray are acceptable as measurable lesions when they are clearly defined and surrounded by aerated lung. However, CT is preferable.

Conventional CT and MRI: This guideline has defined measurability of lesions on CT scan based on the assumption that CT slice thickness is 5 mm or less. If CT scans have slice thickness greater than 5 mm, the minimum size for a measurable lesion should be twice the slice thickness. MRI is also acceptable in certain situations (e.g. for body scans).

Use of MRI remains a complex issue. MRI has excellent contrast, spatial, and temporal resolution; however, there are many image acquisition variables involved in MRI, which greatly impact image quality, lesion conspicuity, and measurement. Furthermore, the availability of MRI is variable globally. As with CT, if an MRI is performed, the technical specifications of the scanning sequences used should be optimized for the evaluation of the type and site of disease. Furthermore, as with CT, the modality used at follow-up should be the same as was used at baseline and the lesions should be measured/assessed on the same pulse sequence. It is beyond the scope of the RECIST guidelines to prescribe specific MRI pulse sequence parameters for all scanners, body parts, and diseases. Ideally, the same type of scanner should be used and the

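### Target-lesion progression in 6.4.4.1 has no minimum absolute increase, so when the reference sum is below 25 mm a change of a few millimetres can be called progression

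*Combined protocol and SAP*

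**What the plan says.** Section 6.4.4.1 defines progression of target lesions as "At least a 20% increase in the sum of diameters of target lesions taking as reference the smallest sum on study". Baseline serves as the comparator when no later sum is lower, and a new lesion also counts as progression. No absolute increase is required there, in 6.4.4.3 (best overall response), or anywhere else in the document.

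Section 6.4.2 makes a non-nodal lesion measurable "as ≥ 10 mm with CT scan". Target lesions are taken "up to a maximum of 2 lesions per organ and 5 lesions in total", with no lower limit on their number, so one 10 mm lesion can be the entire sum. On slice thickness, 6.4.2 has "CT scan slice thickness recommended to be no greater than 5 mm" for nodes, and 6.4.3 rests measurability on "the assumption that CT slice thickness is 5 mm or less".

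Progression has two consequences. Section 6.4.4.3 counts best response only up to progression, and 3.9.1 lists "Progressive Disease" among the off-treatment criteria. Section 3.7, however, lets patients with clinical benefit continue at the PI's discretion, without saying whether this applies after progression. Sections 3.7 and 6.4 name RECIST 1.1 as the standard.

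**The concern.** A purely relative threshold shrinks with the tumour sum, while the error of a diameter reading need not. Below some sum, 20% is no larger than ordinary variation between readings. Because the reference is the smallest sum so far, one low reading stays as the comparator for all later scans, and the chance of a false call accumulates.

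A false progression would be a PFS event in a patient whose tumour has not grown. PFS is a secondary objective, and the documents give no other definition of progression. In a patient who has just had a first partial response, a false progression at the next scan closes the best-response window. It could thereby prevent confirmation, which 6.4.4.3 mentions but does not spell out. Section 8 decides each cohort on 3 or more responses in 20, so single patients matter.

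**Working it through.** **The plan's own figure.** Section 8 gives no false-progression rate. Its early-termination probability reproduces: 0.95^13 = 0.513, as stated. The exact two-stage calculation for 0/13 then 3/20 gives alpha 0.074 and power 0.903, within the stated 0.10 and 0.90. The sample size is not in question.

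**Increase needed for progression.** The present rule needs 0.20 × reference sum. With a 5 mm minimum it needs max(0.20 × reference sum, 5 mm). The two coincide from 5/0.20 = 25 mm upwards.

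| Reference sum (mm) | 20% rule (mm) | With 5 mm minimum (mm) |
|---|---|---|
| 7 | 1.4 | 5 (71%) |
| 10 | 2.0 | 5 (50%) |
| 15 | 3.0 | 5 (33%) |
| 20 | 4.0 | 5 (25%) |
| 25 | 5.0 | 5 (20%) |
| 50 | 10.0 | 10 (20%) |

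**False progression in a stable lesion.** Assumptions: true diameter constant; independent normal error with SD s at every reading; s = 1 mm, range 0.5 to 1.5 mm (not from the documents); progression called when a reading exceeds the smallest earlier reading by at least 20%. Scans follow every two cycles (6 weeks), so the fourth is at about 24 weeks.

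*First scan, ignoring the entry rule.* P(X1 ≥ 1.2 × X0) = 1 − Φ(0.2 × 10 / (s√(1 + 1.2²))). With s = 1 this is 1 − Φ(2/1.562) = 10%.

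*First scan, with the entry rule.* Section 6.4.2 admits a lesion only if it reads at least 10 mm at baseline. That removes about half of the simulated baselines, namely the low ones that cause most first-scan calls. The probability falls to 0.5%.

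*Later scans.* By simulation for one lesion of true diameter 10 mm, baseline reading at least 10 mm, cumulative:

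| Scan | s = 0.5 | s = 1 | s = 1.5 |
|---|---|---|---|
| 1st | <0.1% | 0.5% | 2.6% |
| 2nd | 0.5% | 11% | 23% |
| 4th | 3% | 38% | 63% |
| 4th, with 5 mm minimum | 0% | 0.1% | 5% |

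A single stable non-nodal 15 mm lesion gives 7% by the second scan at s = 1, and a single 20 mm lesion about 1.5%.

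**After a response.** Let a lesion shrink from a true 10 mm to a true 7 mm and stay there. The chance that the second reading at 7 mm exceeds the first by 20% is 1 − Φ(1.4/(s√2.44)), which is 1 − Φ(0.90) = about 18% at s = 1. Among patients whose first reading qualifies as a partial response, the readings are selected to be low and the figure is about 26% (simulation, s = 1).

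**The case against.** The strongest reply is that this is a corner case. The rule acts on the sum of up to five lesions, chosen for size and reproducible measurement, in patients with advanced disease. At s = 1 mm, two stable 15 mm lesions give only about 0.9% by the second scan. No figure in the documents shows how many patients would have a reference sum below 25 mm. This stands, and it limits the reach of the point. It does not remove it, because the entry criteria admit such patients and a good response moves others into that range.

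The protocol also cites RECIST 1.1 as its standard. The guideline's text is not in the documents, so whether it supplies a minimum cannot be judged here. The written definition in 6.4.4.1 does not, and the reader cannot tell which governs if they differ.

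A reader might go further in four ways that the documents do not support:

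- **A 10% false-progression rate at the first scan and 23% by the second.** These figures ignore the requirement of a baseline reading of at least 10 mm.
- **That CT cannot resolve 2 mm because slices may be 5 mm thick.** The 5 mm is a ceiling and a measurability assumption. It is not the error of an in-plane diameter, and serves only as a yardstick.
- **A loss of power for the 3-of-20 rule.** Stable patients are non-responders under either definition. For an eligible 10 mm lesion shrinking to 8 mm at the first scan, false progression there is below 0.1% even at s = 1.5 mm. If 10% or 20% of true responders were lost, power would fall from 90.3% to 85.4% or 78.6%, but nothing in the documents yields those fractions.
- **That such a call always ends treatment.** Section 3.9.1 points that way, but the discretion sentence in 3.7 leaves it open.

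**Conclusion.** The point holds for reference sums below 25 mm. There the written rule lets a change of 1.4 to just under 5 mm count as progression, depending on the sum (7 mm upwards). For the smallest eligible single lesion the first scan is nearly safe, but the error accumulates to 11% by the second scan and 38% by the fourth at an assumed reader SD of 1 mm. The results are sensitive to that SD: 3% to 63% by the fourth scan over 0.5 to 1.5 mm. They also assume independent normal errors and no true change.

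The main effect is on PFS, which Section 8 treats as exploratory, and on small-sum responders who could lose confirmation. The number of such patients is unknown, and the operating characteristics in Section 8 stand as written.

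**What to change.** In the endpoint definition in 6.4.4.1, require that the sum of target diameters rise by at least 5 mm in absolute terms as well as by at least 20% over the smallest sum on study. Check the wording against the RECIST 1.1 guideline named in 3.7 and 6.4, and state which text governs if they differ.

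The cost is one clause, with no change to sample size or scan schedule. The downside is that true growth in very small lesions may be called one scan later. New lesions and unequivocal progression of non-target lesions would still count at once, and reference sums of 25 mm or more are treated as now.

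Separately, the discretion sentence in 3.7 and the off-treatment criteria in 3.9.1 must be reconciled, so that it is clear what follows from a progression call. Which of them should apply is for the sponsor to decide.

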6.4.4.2 Evaluation of non-target lesions**

Complete Response (CR): Disappearance of all non-target lesions and normalization of tumor marker level. All lymph nodes must be non-pathological in size (<10mm short axis).

Non-CR/Non-PD: Persistence of one or more non-target lesions and/or maintenance of tumor marker level above the normal limits.

Progression (PD): Appearance of one or more new lesions. Unequivocal progression of existing non-target lesions

All other lesions (or sites of disease), including pathological lymph nodes should be identified as **non-target lesions and should also be recorded at baseline. Measurements are not required, and these lesions should be followed as “present”, “absent”, or in rare cases “unequivocal progression.”

6.4.4.3 Evaluation of Best Overall Response

The best overall response is the best response recorded from the start of the treatment until disease progression/recurrence (taking as reference for progressive disease the smallest measurements recorded since the treatment started). The patient's best response assignment will depend on the achievement of both measurement and confirmation criteria.

Target Lesions	Non-Target Lesions	New Lesions	Overall Response
CR	CR	No	CR
CR	Non-CR/Non-PD	No	PR
CR	Not evaluated	No	PR
PR	Non-PD or not all evaluated	No	PR
SD	Non-PD or not all evaluated	No	SD
Not all evaluated	Non-PD	No	NE
PD	Any	Yes or No	PD
Any	PD	Yes or No	PD
Any	Any	Yes	PD

6.5 TOXICITY CRITERIA

The following adverse event management guidelines are intended to ensure the safety of each patient while on the study. The descriptions and grading scales found in the revised NCI Common Terminology Criteria for Adverse Events (CTCAE) version 4.0 will be utilized for AE reporting. All appropriate treatment areas should have access to a copy of the CTCAE version 4.0. A copy of the CTCAE version 4.0 can be downloaded from the CTEP web site (http://ctep.cancer.gov/protocolDevelopment/electronic_applications/ctc.htm#ctc_40).

7 SAFETY REPORTING REQUIREMENTS/DATA AND SAFETY MONITORING PLAN

7.1 DEFINITIONS

7.1.1 Adverse Event

An adverse event is defined as any reaction, side effect, or untoward event that occurs during the course of the clinical trial associated with the use of a drug in humans, whether or not the event is considered related to the treatment or clinically significant. For this study, AEs will include events reported by the patient, as well as clinically significant abnormal findings on physical examination or laboratory evaluation. A new illness, symptom, sign or clinically significant laboratory abnormality or worsening of a pre-existing condition or abnormality is considered an AE. All AEs must be recorded on the AE case report form unless otherwise noted above in Section 6.2.

All AEs, including clinically significant abnormal findings on laboratory evaluations, regardless of severity, will be followed until return to baseline or stabilization of event. Serious adverse events that occur more than 30 days after the last administration of investigational agent/intervention and have an attribution of at least possibly related to the agent/intervention should be recorded and reported as per sections **7.3, 7.4**.

An abnormal laboratory value will be considered an AE if the laboratory abnormality is characterized by any of the following:

- Results in discontinuation from the study
- Is associated with clinical signs or symptoms
- Requires treatment or any other therapeutic intervention
- Is associated with death or another serious adverse event, including hospitalization.
- Is judged by the Investigator to be of significant clinical impact
- If any abnormal laboratory result is considered clinically significant, the investigator will provide details about the action taken with respect to the test drug and about the patient's outcome.

7.1.2 Suspected adverse reaction

Suspected adverse reaction means any adverse event for which there is a reasonable possibility that the drug caused the adverse event. For the purposes of IND safety reporting, 'reasonable possibility' means there is evidence to suggest a causal relationship between the drug and the adverse event. A suspected adverse reaction implies a lesser degree of certainty about causality than adverse reaction, which means any adverse event caused by a drug.

7.1.3 Unexpected adverse reaction

An adverse event or suspected adverse reaction is considered "unexpected" if it is not listed in the investigator brochure or is not listed at the specificity or severity that has been observed; or, if an investigator brochure is not required or available, is not consistent with the risk information described in the general investigational plan or elsewhere in the current application.

"Unexpected" also refers to adverse events or suspected adverse reactions that are mentioned in the investigator brochure as occurring with a class of drugs or as anticipated from the pharmacological properties of the drug, but are not specifically mentioned as occurring with the particular drug under investigation.

7.1.4 Serious

An Unanticipated Problem or Protocol Deviation is serious if it meets the definition of a Serious Adverse Event or if it compromises the safety, welfare or rights of subjects or others.

7.1.5 Serious Adverse Event

An adverse event or suspected adverse reaction is considered serious if in the view of the investigator or the sponsor, it results in any of the following:

- Death,
- A life-threatening adverse drug experience
- Inpatient hospitalization or prolongation of existing hospitalization

- Persistent or significant incapacity or substantial disruption of the ability to conduct normal life functions
- A congenital anomaly/birth defect.
- Important medical events that may not result in death, be life-threatening, or require hospitalization may be considered a serious adverse drug experience when, based upon appropriate medical judgment, they may jeopardize the patient or subject and may require medical or surgical intervention to prevent one of the outcomes listed in this definition.

7.1.6 Disability

A substantial disruption of a person's ability to conduct normal life functions.

7.1.7 Life-threatening adverse drug experience

Any adverse event or suspected adverse reaction that places the patient or subject, in the view of the investigator or sponsor, at immediate risk of death from the reaction as it occurred, i.e., it does not include a reaction that had it occurred in a more severe form, might have caused death.

7.1.8 Protocol Deviation (NIH Definition)

Any change, divergence, or departure from the IRB approved research protocol.

7.1.9 Non-compliance (NIH Definition)

The failure to comply with applicable NIH Human Research Protections Program (HRPP) policies, IRB requirements, or regulatory requirements for the protection of human research subjects.

7.1.10 Unanticipated Problem

Any incident, experience, or outcome that:

- Is unexpected in terms of nature, severity, or frequency in relation to
 - (a) the research risks that are described in the IRB-approved research protocol and informed consent document; Investigator's Brochure or other study documents, and
 - (b) the characteristics of the subject population being studied; **AND**
- Is related or possibly related to participation in the research; **AND** Suggest that the research places subjects or others at a *great risk of harm* (including physical, psychological, economic, or social harm) than was previously known or recognized.

7.2 NCI-IRB AND CLINICAL DIRECTOR (CD) REPORTING

7.2.1 NCI-IRB and NCI CD Expedited Reporting of Unanticipated Problems and Deaths

The Protocol PI will report in the NIH Problem Form to the NCI-IRB and the NCI Clinical Director:

- All deaths, except deaths due to progressive disease
- All Protocol Deviations

- All Unanticipated Problems
- All non-compliance

Reports must be received within 7 days of PI awareness via iRIS.

7.2.2 NCI-IRB Requirements for PI Reporting at Continuing Review

The protocol PI will report to the NCI-IRB:

1. A summary of all protocol deviations in a tabular format to include the date the deviation occurred, a brief description of the deviation and any corrective action.
2. A summary of any instances of non-compliance
3. A tabular summary of the following adverse events:
 - All Grade 2 **unexpected** events that are possibly, probably or definitely related to the research;
 - All Grade 3 and 4 events that are possibly, probably or definitely related to the research;
 - All Grade 5 events regardless of attribution;
 - All Serious Events regardless of attribution.

NOTE: Grade 1 events are not required to be reported.

7.2.3 NCI-IRB Reporting of IND Safety Reports

Only IND Safety Reports that meet the definition of an unanticipated problem will need to be reported to the NCI IRB.

7.3 IND SPONSOR REPORTING CRITERIA

An investigator must **immediately** report to the sponsor, using the mandatory MedWatch form 3500a, any serious adverse event, whether or not considered drug related, including those listed in the protocol or investigator brochure and must include an assessment of whether there is a reasonable possibility that the drug caused the event.

- All Grade 5 (fatal) events (except death due to progressive disease) must be reported via email within 24 hours. A complete report must be submitted within one business day.
- All other serious adverse events including deaths due to progressive disease must be reported within one business day

Study endpoints that are serious adverse events (e.g. all-cause mortality) will be reported in accordance with the protocol and study sponsor.

Events will be submitted to the Center for Cancer Research (CCR) at: [contact] and to the CCR PI and study coordinator.

7.3.1 Reporting Pregnancy

7.3.1.1 Maternal exposure

If a patient becomes pregnant during the course of the study, the study treatment should be discontinued immediately and the pregnancy reported to the Sponsor. The potential risk of exposure of the fetus to the investigational agent(s) or chemotherapy agents (s) should be documented in box B5 of the MedWatch form “Describe Event or Problem”.

Pregnancy itself is not regarded as an SAE. However, as patients who become pregnant on study risk intrauterine exposure of the fetus to agents which may be teratogenic, the CCR is requesting that pregnancy should be reported in an expedited manner as **Grade 3 “Pregnancy, puerperium and perinatal conditions - Other (pregnancy)”** under the ***Pregnancy, puerperium and perinatal conditions*** SOC.

Congenital abnormalities or birth defects and spontaneous miscarriages should be reported and handled as SAEs. Elective abortions without complications should not be handled as AEs. The outcome of all pregnancies (spontaneous miscarriage, elective termination, ectopic pregnancy, normal birth, or congenital abnormality) should be followed up and documented.

If any pregnancy occurs in the course of the study, then the investigator should inform the Sponsor within 1 day, i.e., immediately, but **no later than 24 hours** of when he or she becomes aware of it.

The designated Sponsor representative will work with the investigator to ensure that all relevant information is provided to the Sponsor within 1 to 5 calendar days for SAEs and within 30 days for all other pregnancies.

The same timelines apply when outcome information is available.

